Aim 2: To estimate decrease in P. Acnes burden with preop skin preps compared to the contralateral side.

We hypothesize that three day preoperative application of 5% topical benzoyl peroxide will decrease patient's P. Acnes bacterial burden in comparison to chlorhexidine (positive control) and in comparison to the nonoperative shoulder (negative control).

- 2

* Discuss the research design including but not limited to such issues as: probability of group assignment, potential for subject to be randomized to placebo group, use of control subjects, etc.:

After surgical posting, patients will be randomized to chlorhexidine or benzoyl peroxide group. The solutions used will be 5% benzoyl peroxide emollient foam and 4% chlorhexidine gluconate skin cleanser. Participants will be instructed to conduct skin wash using the appropriate solution in the shower over the operative shoulder and axilla for three mornings prior to surgery (pre op day -2, pre op day -1, and morning of surgery). Specific instructions will include leaving the solution on the skin for three minutes and avoiding contact with eyes, ears, and mouth. Proper technique will be demonstrated at time of patient recruitment and given as a handout with the wash solution provided. A reminder phone call will occur two days before surgery to remind patients of proper procedure to improve compliance. On the day of surgery, patients be interviewed about pre-operative compliance.

On the day of surgery, two cultures will be taken in three separate sites on both shoulders (anterior, lateral, and posterior) using a detergent scrub technique, the current dermatologic standard for biopsy of the deep sebaceous glands. (3,11) This procedure is typically performed on the skin of awake patients and causes minimal pain and skin irritation. Cultures will be evaluated in our lab. We will also test for hemolysis as a possible indicator of a more virulent strain in the literature.

The research team may take photos of the shoulder skin being swabbed. Photos will not include the facial or defining characteristics. Photos may be taken either in the clinic at time of recruitment or in the operating room when samples are being taken.

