Inclusion criteria: all patients undergoing open shoulder surgery or shoulder arthroscopy. Exclusion criteria: anyone with a history of allergic reaction to chlorhexidine or benzoyl peroxide. Anyone with a history of previous shoulder infection, current open skin lesions around the shoulder or the use of current anti-acne medications around the shoulder.

Healthy volunteer portion: Healthy volunteers will respond to the study from fliers on campus. A cotton swab test on both shoulders will be performed prior to any treatment. If a threshold of P. Acnes is met (>1000 CFUs) then volunteers will be randomized to the same two groups and retested after three days of unilateral treatment. Finally, volunteers will undergo repeat cotton swab testing one week after 3 day wash was finalized.

3 * Describe the relevant prior experience and gaps in current knowledge. Describe any relevant preliminary data:

We have no preliminary data at this institution. Current P. Acnes shoulder burden is estimated to be 36% based on recent literature with a periprosthetic infection rate is at least 1-2% with this number expected to increase as more shoulder surgery is expected with the aging population. Economic impact after a shoulder surgical infection is tremendous with additional estimated hospital costs of over \$17,000 per infection not including the impact from wages lost (12).

4 * Provide the scientific or scholarly background, rationale, and significance of the research and how it will add to existing knowledge:

P.acnes is a gram-positive anaerobic bacillus that resides nonpathogenically in the sebaceous glands associated with hair follicles. P.acnes frequently becomes a pathogenic causing infection after arthroscopic and open shoulder procedures. Untreated infections of this nature present with shoulder pain, glenohumeral arthrosis, and arthroplasty failure months or years after a procedure(1). P.acnes forms a biofilm on implant surfaces; cultures taken at the time of surgical revision of failed shoulder arthroplasties are commonly positive for the bacteria(2).

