- 2 * Provide the plan for data analysis. Include in the description the types of comparisons that are planned (e.g., comparison of means, comparison of proportions, regressions, analysis of variance, etc.), which is the primary comparison/analysis, and how the analyses proposed will relate to the primary purposes of the study:

Patient will be asked how many times they actually used the skin prep. We will utilize both intention-to-treat and as-treated analyses. We will employ a linear regression based on level of compliance (1 day, 2 day etc.). Paired t-test will be used as a comparison of mean CFUs to the contralateral side (negative control) and the primary outcome will be based on an aggregate chi-square comparison of proportions between chlorohexidine and benzoyl peroxide groups.

ID: VIEW4E02806052800
Name: v2_Sample Size and Data Analysis

Sharing of Results

- 1 * Describe whether results (study results or individual subject results, such as results of investigational diagnostic tests, genetic tests, or incidental findings) will be shared with subjects or others (e.g., the subject's primary care physicians) and if so, describe how it will be shared:

The results of specific tests and the overall study will not be shared with participants. The results will not affect the standard of care for each patient.

ID: VIEW4E02808CBD800
Name: v2_Sharing of Results

Research with Drugs or Biologics

You indicated on the "Type of Research" page that your study involves use of unapproved drug(s)/biologic(s) or approved drug(s)/biologic(s) whose use is specified in the protocol AND/OR evaluation of food(s) or dietary supplement(s) to diagnose, cure, treat, or mitigate a disease or condition.

- 1 * List all drugs/biologics to be administered in this study. Be sure to list each drug/biologic with its generic name only.

Drug Name	FDA Approved	IND Number	PI IND Holder
View Benzoyl Peroxide	yes		no
View Chlorhexidine	yes		no

- 2 * Attach the drug package insert or investigational drug brochure for the drugs being administered in this study:

5% BPO Label.jpg	8/26/2015 10:51 AM	8/26/2015 10:51 AM
Chlorhex 4%.png	3/30/2015 9:48 PM	6/17/2015 10:30 AM

- 3 If more than one drug is administered, discuss the risk implications of drug/therapy interactions:
Drugs will not be administered simultaneously

- 4 * Will you be using Investigational Drug Services?

Yes No

ID: VIEW4E0916E6E1400
Name: v2_Research with Drugs or Biologics

Drug or Biologic Storage and Handling

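### The protocol does not say how the treated shoulder is chosen in healthy volunteers, which leaves their treated-versus-untreated contrast open to bias; randomise the side together with the wash.

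*Combined protocol and SAP*

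**What the plan says.** Justification, Objective, & Research Design, item 2, sets out the volunteer part in four steps.

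- Baseline: "A cotton swab test on both shoulders will be performed prior to any treatment".
- Entry: a P. acnes count above 1000 CFU is required. The text does not say whether one shoulder, both, or the treated one must exceed it.
- Allocation: those who pass are randomised between the two washes and "retested after three days of unilateral treatment".
- Late follow-up: "volunteers will undergo repeat cotton swab testing one week after 3 day wash was finalized".

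Only the wash is described as randomised. Nothing says who picks the shoulder, by what rule, or whether the pick comes before or after the swab result is known. In surgical patients the wash goes on the operative shoulder, so their side is fixed.

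The untreated shoulder serves the second aim in item 1 of the same section: "To estimate decrease in P. Acnes burden with preop skin preps compared to the contralateral side". Sample Size and Data Analysis, item 2, names the method: "Paired t-test will be used as a comparison of mean CFUs to the contralateral side (negative control"). It mentions no baseline adjustment. The same item makes the primary analysis a chi-square test between the two wash groups. Item 1 there sets 160 participants, about a quarter of them volunteers.

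**The concern.** A treated-versus-untreated contrast within a person estimates the wash effect only if the two shoulders would have had the same expected count without the wash. Randomising the side guarantees this. Choosing the side does not.

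Two kinds of choice matter here. A fixed preference, such as always the dominant arm, carries any stable difference between sides into the contrast. A choice made on the baseline count is worse, because the treated shoulder then starts higher by construction, partly from a real side difference and partly from swab error. The protocol's order of steps (swab both shoulders, apply a threshold, then treat one) leaves room for that second choice without requiring it.

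Volunteers are the only participants for whom a pre-wash swab of both shoulders is described, and the only ones whose treated side is free. Theirs is therefore the one within-person contrast in this trial that could be fully randomised. A side chosen on the count cannot be randomised afterwards.

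**Working it through.** **The plan's own figure.** The documents give no figure for the side contrast. The stated sample size belongs to the primary comparison: p1 = 0.36, p2 = 0.12, two-sided alpha 0.05, power 0.80, mean proportion 0.24.

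n per group = [1.960 × √(2 × 0.24 × 0.76) + 0.842 × √(0.36 × 0.64 + 0.12 × 0.88)]² / 0.24² = (1.184 + 0.488)² / 0.0576 ≈ 48.5, so 49 per group and 98 in total. This matches the plan, and randomising the side does not alter it.

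**Assumed inputs for the side contrast (none is in the documents).** Log10 CFU is normal with mean 3 (1000 CFU) and SD 1. The correlation r between two swabs of the same shoulder is 0.6 to 0.8. The correlation c between the two shoulders is 0.3 to 0.6. The wash has no effect. The plan compares mean CFUs; the log scale is a choice made for this check.

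**If the higher-count shoulder is treated.** Let G be the mean baseline gap, treated minus untreated, among those who enter. Selection uses the baseline counts only, so the expected retest gap is a fixed fraction of the baseline gap:

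- post-wash difference = G × (r − c)/(1 − c)
- difference in change = −G × (1 − r)/(1 − c)

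A simulation of the entry rule gives these values of G:

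| Entry rule | c = 0.3 | c = 0.6 |
|---|---|---|
| either shoulder above 3 log10 | 1.07 | 0.80 |
| both shoulders above 3 log10 | 0.65 | 0.56 |

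The extremes over the assumed ranges are:

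- Post-wash difference, largest (either, c = 0.3, r = 0.8): 1.07 × 0.5/0.7 = +0.76. The simulation gives +0.77.
- Post-wash difference, smallest (c = r = 0.6): 0, because the shoulders then have no stable difference.
- Difference in change, largest (either, c = r = 0.6): −0.80 × 0.4/0.4 = −0.80.
- Difference in change, smallest (both, c = 0.3, r = 0.8): −0.65 × 0.2/0.7 = −0.19. The simulation gives −0.18.

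The post-wash difference hides a real effect. The difference in change creates a false one by regression to the mean. With a randomised side, both are zero within simulation error.

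**If a fixed side is always treated.** A separate check assumed a person SD of 1, side-to-side and swab SDs of 0.3 to 0.5, and 0.2 log10 more on the treated side. The post-wash difference was biased by 0.16 to 0.22 log10. The difference in change stayed within 0.04 log10 of zero. For the higher-count rule, the same check gave 0.15 to 0.53 log10 in each direction.

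**What a random side costs against the threshold.** With the mean at the threshold:

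- P(both above) = 1/4 + arcsin(c)/(2π) = 0.299 for c = 0.3 and 0.352 for c = 0.6.
- By symmetry, P(either above) = 1 − P(both above) = 0.701 and 0.648.
- If either shoulder qualifies and the side is random, the share treating a shoulder at or below 1000 CFU is ½ × (0.701 − 0.299)/0.701 = 29% for c = 0.3, and ½ × (0.648 − 0.352)/0.648 = 23% for c = 0.6.

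**The case against.** **The documents are silent.** A reader might infer that the side is not randomised, or that the shoulder that passed the threshold is the one treated. Neither is stated. The volunteer consent form and the wash instructions are listed but not reproduced, and either could name a side. This stands: the point is an unstated rule, and treating the higher-count shoulder is only one possibility. The design section is still where the rule belongs.

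**Aim 2 may be about patients.** The hypothesis calls the negative control the nonoperative shoulder, and the analysis section does not say that volunteers enter the paired t-test. This stands in part. Volunteers are treated on one side and swabbed on both before treatment, and no other analysis of their untreated shoulder is described.

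**The stated test would err against the wash.** Under the higher-count rule a post-wash paired test understates the effect, and the bias is small beside the 1.9 log fall that the background cites. The first part is right, but Aim 2 is an estimate, so bias in either direction matters. The cited fall followed one week of foam on the back, so it gives scale and is not the effect to expect after three days on the shoulder.

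**The bilateral baseline could repair it.** A change from baseline largely removes a stable side difference, but not regression to the mean when the side was chosen on the count. Adjusting for both baselines as covariates can remove that too in an idealised linear model. However, no treated shoulder would then have the lower baseline, so the result rests on extrapolation. No adjustment is planned.

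**The primary result.** A reader might infer that the comparison of the two washes is compromised. It is not, provided that the same side rule applies in both arms and is settled without knowledge of the wash.

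**Conclusion.** The concern holds as a gap with a known remedy: the protocol does not say how the treated shoulder is chosen in volunteers, and its stated side contrast is unprotected if the choice is not random.

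Under the assumed inputs, treating the higher-count shoulder shifts the post-wash difference by 0 to about +0.8 log10 and a difference in change by about −0.2 to −0.8 log10, with no wash effect at all. These sizes depend mainly on the correlation between shoulders, which the documents do not give. The directions are what to rely on.

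The reach is limited to a secondary contrast in about 160/4 = 40 people. In surgical patients the operation fixes the side, so this change does not protect Aim 2 there. It should still be made, because it is cheap and cannot be recovered once volunteers have been treated.

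**What to change.** 1. Randomise left or right for each volunteer on the same list as the wash, balanced within each wash arm and generated independently of the swab results.
2. State the entry threshold so that it does not depend on the allocated side: either shoulder above 1000 CFU, or both.
3. State whether volunteers enter the paired analysis. Analyse their side contrast with adjustment for the baseline counts of both shoulders, which are already collected.

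The cost is one more column on the list, one line in the volunteer instructions, and a trade-off on the threshold. Under the assumptions above:

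- If either shoulder qualifies, about a quarter of volunteers (23 to 29%) would treat a shoulder at or below 1000 CFU, with less room to show a fall.
- If both must qualify, that loss disappears, but fewer people pass. Entering 40 volunteers would take about 40/0.352 = 114 to 40/0.299 = 134 swabbed, against about 40/0.701 = 57 to 40/0.648 = 62 under the either rule. The screening total of 200 in Participant Selection should be checked against the rule chosen.

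The sample size of 98 for the primary comparison is unchanged.

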The patient him or herself (as opposed to a proxy) should be consented. The research staff will endeavor to answer all questions posed by the patient and his/her family to ensure their understanding of the protocol. A limited number of questions will be asked of all patients after they are introduced to the study and have reviewed the consent form. These questions assess the person's understanding of the study and what it means to participate, their appreciation of the consequences of participation, and their ability to consider alternatives to participation. The Research Coordinator will ask the questions and determine the appropriateness of the responses. If the Research Coordinator is at all unsure about the patient's ability to consent s/he will consult with the study site PI. If a patient is unable to consent, then he/she will be excluded from the study.

Recognizing that consent is an ongoing process, the study team will encourage the participants to ask additional questions that may arise during the course of their participation in the study.

The only thing different than standard treatment/surgery is the additional skin prep three days prior to surgery. Chlorhexidine scrub is standard for hip and knee replacements but we believe have limited effect on P. Acnes. Benzoyl Peroxide may treat this better. Anesthesia and antibiotic prophylaxis are standardized. Intraoperative skin prep is standardized as well. We will perform a standard dermatologic detergent scrub technique on both shoulders as a correlate of the P. Acnes burden in the sebaceous glands just prior to intraoperative skin prep. This technique is analogous to using a cotton skin swab.
- * Describe all procedures already being performed for diagnostic or treatment purposes (if not applicable to the study, enter "N/A"):**

Patients will receive standard of care for all diagnostic or treatment purposes. They will be indicated for shoulder surgery as is the usual protocol. All procedures in the operating room will be under usual protocol including skin prep, sterile procedure as well as a usual post operative protocol and follow up. Patients will be followed to document infection, as would be standard of care as well. Monitoring will be at 2 weeks, 6 weeks, 3 and 6 months as well as 12 months which are standard visits after shoulder surgery and based on the standard protocol of asking the patient about their symptoms. No additional testing will be performed. Patient demographics will be reviewed from the chart.
- * Describe the duration of an individual participant's participation in the study:**

Patients will be monitored for the standard signs of infection for one year after shoulder surgery.

Healthy Volunteers will participate for about 12 days.
- * Describe the amount of time it will take to complete the entire study:**

24 months total. 6 month enrollment period. 12 month follow up. 6 month data analysis and manuscript preparation.
- * Describe any additional participant requirements:**

N/A

ID: VIEW4E0280585B400
Name: v2_Study Procedures

Sample Size and Data Analysis

If you uploaded a separate research protocol document in the 'Research Protocol' page, cite the applicable section and page numbers from that document in the answer boxes below.

- 1 * Provide the rationale and sample size calculations for the proposed target population:
Power analysis. In primary shoulder surgeries, the overall incidence of P. Acnes is 36% in a recent series. We expect a 2/3 decrease in intraoperative incidence. Ninety eight patients are necessary, a 20% attrition rate is expected so a goal of 160 people to be recruited total and about 1/4 to be healthy volunteers.

See below from Stata/SE 13.0 for Mac (64-bit Intel), Revision 17 Jun 2013

```
power twoproportions 0.36 0.12, test(chi2)
Performing iteration ...
Estimated sample sizes for a two-sample proportions test
Pearson's chi-squared test
Ho: p2 = p1 versus Ha: p2 != p1
```

Study parameters:

```
alpha = 0.0500
power = 0.8000
delta = -0.2400 (difference)
p1 = 0.3600
p2 = 0.1200
```

```
Estimated sample sizes: N = 98
N per group = 49
```

- 2 * Provide the plan for data analysis. Include in the description the types of comparisons that are planned (e.g., comparison of means, comparison of proportions, regressions, analysis of variance, etc.), which is the primary comparison/analysis, and how the analyses proposed will relate to the primary purposes of the study:

Patient will be asked how many times they actually used the skin prep. We will utilize both intention-to-treat and as-treated analyses. We will employ a linear regression based on level of compliance (1 day, 2 day etc.). Paired t-test will be used as a comparison of mean CFUs to the contralateral side (negative control) and the primary outcome will be based on an aggregate chi-square comparison of proportions between chlorohexidine and benzoyl peroxide groups.

ID: VIEW4E02806052800
Name: v2_Sample Size and Data Analysis

Sharing of Results

- 1 * Describe whether results (study results or individual subject results, such as results of investigational diagnostic tests, genetic tests, or incidental findings) will be shared with subjects or others (e.g., the subject's primary care physicians) and if so, describe how it will be shared:

The results of specific tests and the overall study will not be shared with participants. The results will not affect the standard of care for each patient.

ID: VIEW4E02808CBD800
Name: v2_Sharing of Results

Research with Drugs or Biologics

You indicated on the "Type of Research" page that your study involves use of unapproved drug(s)/biologic(s) or approved drug(s)/biologic(s) whose use is specified in the protocol AND/OR evaluation of food(s) or dietary supplement(s) to diagnose, cure, treat, or mitigate a disease or condition.

- 1 * List all drugs/biologics to be administered in this study. Be sure to list each drug/biologic with its generic name only.

Drug Name	FDA Approved	IND Number	PI IND Holder
View Benzoyl Peroxide	yes		no
View Chlorhexidine	yes		no

- 2 * Attach the drug package insert or investigational drug brochure for the drugs being administered in this study:

5% BPO Label.jpg	8/26/2015 10:51 AM	8/26/2015 10:51 AM
Chlorhex 4%.png	3/30/2015 9:48 PM	6/17/2015 10:30 AM

- 3 If more than one drug is administered, discuss the risk implications of drug/therapy interactions:
Drugs will not be administered simultaneously

- 4 * Will you be using Investigational Drug Services?

Yes No

ID: VIEW4E0916E6E1400
Name: v2_Research with Drugs or Biologics

Drug or Biologic Storage and Handling

- 4.1 * Do you have a plan regarding access controls for essential and appropriate research personnel?

Yes No

- 4.2 * Will you have procedures for verifying physical access to the drugs(s)?

Yes No

- 4.3 * Will you label the drug(s) so that it is (they are) used appropriately for the study?

Yes No

4.4

* Will there be an establishment of a drug transfer process both into and out of the research site?

Yes No

4.5 * Will the storage of the drug(s) be in a secure environment and include locks on doors and controlled access?

Yes No

4.6 * Do you have a plan for only allowing trained personnel to administer the drug(s)?

Yes No

4.7 If applicable, will the storage of the drug(s) be at the appropriate temperature, with a storage and temperature log?

Yes No

ID: VIEW4E1D85CC57C00
Name: v2_Drug or Biologic Storage and Handling

Placebos

1 * Is this study placebo controlled?

Yes No

ID: VIEW4E0514EECC00
Name: v2_Placebos

Psychological/Behavioral/Educational Methods & Procedures

You indicated on the "Type of Research" page that your study involves a psychological/behavioral/educational method or procedure such as a survey, questionnaire, interview, or focus group.

1 * Select all behavioral methods and procedures which apply to this study:

Audio or video recording/photographing

ID: VIEW4E09416F57800
Name: v2_Psychological/Behavioral/Educational Methods and Procedures

Audio or Video Recording/Photographs

You indicated that this study involves audio or video recording/photographing.

1

* Indicate the type of recording (check all that apply):

Still Photo

1.1 If Other, specify:

2 * What is the purpose of the recording? (i.e., for therapeutic purposes, to establish treatment fidelity, or to establish reliability of assessments)

The purpose of the photos is to document and characterize the areas being evaluated by the research protocol. Additionally, they will help establish the reliability of assessments.

3 * Could the recording be likely to cause discomfort in participants or cause harm if their confidentiality were breached?

Yes No

4 * How will individuals' identities be protected?

Photos will only include skin area being study without any facial or identifiable characteristics.

ID: VIEW4E094C128C800
Name: v2_Audio or Video Recording / Photographs

Sample Collection/Analysis

You indicated on the "Type of Research" page that your study involves a sample (specimen) collection and/or analysis.

1 * What type of samples will be involved in this study? (Check all that apply)

Prospective (will be collected)

2 * Will genetic analysis/testing be done on any of the samples?

Yes No

- 3 * Will this study involve banking of samples (storing for future research use)?
 Yes No
- 4 * What is the purpose of the sample collection and/or analysis?
 To identify P. Acnes burden
- 5 * Is there the possibility that cell lines will be developed with any of the samples?
 Yes No
- 6 * Will the samples be released to anyone not listed as an investigator on the protocol?
 Yes No
- 6.1 If Yes, give name(s) and affiliation(s):
- 7 * Will the sample material be sold or given to any third parties?
 Yes No
- 7.1 If Yes, give name(s) and address(es):

ID: VIEW4E0E1A4B80000
 Name: v2_Sample Collection/Analysis

Prospective Samples

You indicated that the study involves collection of prospective samples (specimens).

- 1 * What type of sample will be collected? (Check all that apply)
 Other
- 1.1 If Other, specify:
 Skin follicles sampling from a skin swab
- 2 For blood draws, specify the amount drawn, in teaspoons, at each visit and across the course of the subject's entire participation time:
- 3 * What type of samples will be collected? (Check all that apply)
 Samples obtained specifically for research purposes-obtained via a separate collection procedure done solely for the purposes of the study
- 3.1 If Other, specify:
- 4 * How are these samples labeled? For example, do they contain name, initials, dates, Social Security number, medical record number, or other unique code?
 Labeled with unique patient identifier established at time of enrollment
- 5 * Will sample(s) be made available to the research subject (or his/her medical doctor) for other testing?
 Yes No
- 6 * If a participant withdraws from the study, will that participant have the option to get the remaining portion of their sample(s) back?
 Yes No
- 7 * If the participant withdraws, explain how their sample(s) will be handled (For example, will sample(s) be destroyed, anonymized, etc.):
 Samples will be destroyed.
- 8 * Will the samples be destroyed after the study is over?
 Yes No
- 8.1 If No, describe how the samples will be stored, where they will be stored, and for how long.

ID: VIEW4E0E257D60C00
 Name: v2_Prospective Samples

Data Collection/Record Review

You indicated on the "Type of Research" page that your study involves data collection or record review (i.e., chart review, not self-report).

- 1 * What type of data will be collected/analyzed in this study? (Check all that apply)
 Prospective (data is not yet in existence and/or collected)
- 2

* Will this study involve adding data to a registry or database for future use?

Yes No

3 * Will the data be released to anyone not listed as an investigator on the protocol?

Yes No

3.1 If Yes, give name(s) & affiliation(s):

ID: VIEW4E0E25A8CA400
Name: v2_Data Collection / Record Review

Prospective Data

You indicated that the study involves the collection of prospective data.

1 * Where is the data being collected from? (Check all that apply)

Medical records

1.1 If Other, please specify:

2 * What data fields will you have access to/collect for the study? For example, name, initials, date of birth, Social Security number, income, demographic information, family units, housing, etc.

Name
Date of Birth
Gender
Race/Ethnicity

You can also upload a copy of the data fields/variables to be collected for the study:

Name	Created	Modified Date
------	---------	---------------

There are no items to display

ID: VIEW4E0E25B643800
Name: v2_Pro prospective Data

Clinical Trial Registration

You indicated on the "Type of Research" page that your study is a clinical trial.

1 * Does the UM Clinical Trials Registry policy require registration of this trial?

Yes No

2 * Has this trial been registered?

Yes No

ID: VIEW4E093BF078C00
Name: v2_Clinical Trial Registration

Clinical Trial Registration Information

You indicated that this clinical trial has been registered.

1 * Was this trial registered at www.clinicaltrials.gov?

Yes No

2 If no, was this trial registered on a site other than clinicaltrials.gov?

Yes No

2.1 If Yes, specify the name of the other site:

2.2 Provide justification for registering this trial on this site:
To prevent future publishing issues

3 * Registration Number

NCT02510144

ID: VIEW4E093BF1D0800
Name: v2_Clinical Trial Registration Information

Participant Selection

1 * How many local potential participants (or specimens/charts) do you anticipate will be screened for this study? **Screening includes determining potential participants' initial eligibility for and/or interest in a study.**

200

2

* How many participants (or specimens, or charts) will be enrolled/used for this study? **A local prospective participant is considered enrolled in the study when a UM-approved Informed Consent Document (not including separate screening consent forms) is signed.**

Local - the number being enrolled at this site:
160

Worldwide - the number being enrolled total at all sites (including local enrollment):
160

3 * Gender:

Male
Female

4 * Age(s):

18 years and older (Adult)

5 * Race/Ethnicity:

All Races Included

6

* Language(s):
English

6.1 Specify Other:

7 * Are you excluding a specific population, sub-group, or class?

Yes No

7.1 If Yes, indicate your justification for excluding a specific population, sub-group, class, etc.:

ID: VIEW4E0E519C1D000
Name: v2_Participant Selection

Vulnerable Populations

1 * Will you be targeting ANY of the following Vulnerable Populations for enrollment? (Select all that apply)

Employees or Lab Personnel
Students

Only select populations which you will be targeting for enrollment. Do not include populations that may be enrolled incidentally. Enrollment of a vulnerable population is considered to be "targeted" if the study team will be aware that a subject is from a vulnerable group as a result of interaction with the subject or collection of specific information about the subject, and the research team does not wish to exclude them. "Incidental" enrollment is limited to situations where a study team is unaware that a subject is from a vulnerable group.

ID: VIEW4E0E519917800
Name: v2_Vulnerable Populations

Vulnerable Populations - Employees or Lab Personnel

You indicated that employees or lab personnel are included in this study.

1 * Describe how you will ensure participation in this research will not affect employment and prevent undue influence:

Employees may voluntarily elect to participate in the research based on response to the flier. Employees will not be coerced into participating. There is no risk or benefit for an employee to voluntarily participate in the study.

ID: VIEW4E0E5192BA800
Name: v2_Vulnerable Populations - Employees or Lab Personnel

Vulnerable Populations - Students

You indicated that students are included in this study.

1 * Describe the types of students that are included in this study:

Any student on campus may volunteer for the study.

2 * Describe how you will prevent undue influence.

There is no pressure for any student to be recruited for the study.

ID: VIEW4E0E519F32000
Name: v2_Vulnerable Populations - Students

Eligibility

1 * Do you have an existing Eligibility checklist(s) for this study?

Yes No

- 1.1 If Yes, upload here. If you need a template, you can download it by clicking **HERE**. The checklists you upload will also be available under the Documents tab of this application.

Name	Created	Modified Date
------	---------	---------------

There are no items to display

- 1.2 If No, create an eligibility checklist below:

List inclusion criteria (List each Inclusion Criteria individually, using the ADD button):

Number	Criteria
View 1	Age >18
View 2	Patient is indicated for shoulder surgery OR
View 3	Healthy Volunteer

List exclusion criteria (List each Exclusion Criteria individually, using the ADD button):

Number	Criteria
View 1	Patient has history of previous shoulder infection
View 2	Patient has history of allergy to chlorhexidine or benzoyl peroxide
View 3	Patient is currently using other anti-acne medication around the shoulder
View 4	Patient is pregnant, concerned about pregnancy, or lactating (this is part of the usual preoperative blood work)
View 5	Participants will be asked directly about previous topical skin cleanser usage, and asked if there is a history of allergies to either chlorhexidine or benzyl peroxide. If the participant is not a healthy volunteer, their medical records will be screened specifically for allergies to these medications. This procedure is in accordance with current dermatology allergy screening guidelines for both chlorhexidine and benzoyl peroxide.

After entering the inclusion and exclusion criteria above, click the Save link. CICERO will automatically generate a printable Eligibility Checklist for you to use in your research. To review the checklist, click on the resulting link below. This checklist is also available under the Documents tab of this application.

Eligibility Checklist for HP-00064296_4 v1-29-2017-1485704393178(0.01)

ID: VIEW4E0E5185F9000
Name: v2_Eligibility

Recruitment

- 1 * Describe plans for recruitment, including the identification of potential participants (or acquisition of charts/records/samples) and initial interactions with them: (If this study involves the VA please list all sites at which recruitment will take place.):
Patients will be approached for recruitment only after indicated for shoulder surgery in the office.

Volunteers will respond to fliers on campus.

- 2 * Describe measures that will be implemented to avoid participant coercion or undue influence (if not applicable to the study, enter "N/A"):
Potential participants will be approached by both their treating physician and the research coordinator so that any potential clinical care questions can be answered by their treating surgeon. Patients will be reminded that study participation is voluntary, and that the decision to participate or not will not alter the care they receive in any way.

Healthy members of the population will enroll strictly on a volunteer basis.

- 3 * Who will recruit participants (or acquire charts/records/samples) for this study? (Check all that apply)
PI
Study Staff

- 3.1 If you are using a third party, specify Third Party Recruiters:

- 4 Upload any recruitment tools such as screening/telephone scripts and introductory letters (do not upload advertisements here):

Name	Created	Modified Date
------	---------	---------------

There are no items to display

ID: VIEW4E0BCAA0A06C00
Name: v2_Recruitment

Advertising

- 1 * Will you be using advertisements to recruit potential participants?
 Yes No

ID: VIEW4E0BCCF811000
Name: v2_Advertising

Advertising Detail

You indicated that you will be using advertisements to recruit potential participants.

1.1 * Select the mode(s) of advertising (check all that apply):

Print

1.1.1 If Other, specify:

1.2 * Provide exact text of all proposed advertisement(s):

Shoulder infection and bacteria study.

OVERVIEW:

The shoulder infection and bacteria study is volunteer study where participants are asked to undergo a skin swab to review the level of P Acnes bacteria on skin around the shoulder. If a threshold of P Acnes is met, then participants will be randomized to try one of two antibacterial wash to assess reduction in this common bacteria. Participation is for less than two weeks and will require up to three 5-minute swab tests.

KEY ELIGIBILITY CRITERIA:

- Over 18 years of age, any gender or race

FREQUENTLY ASKED QUESTIONS:

- What is the cost of study participation to me?

Answer: None.

- Are there any risks?

Answer: There is a small risk of allergy to chlorhexidine or benzoyl peroxide

- Do I receive any compensation?

Answer: None

- Who is providing grant funding for the study?

Answer: The Orthopaedic department at the University of Maryland School of Medicine.

PARTICIPATE IN THE STUDY:

If you would like to participate in the shoulder infection and bacteria study, please contact us and leave a message at [contact]. A research team member will contact you via phone with more information.

KEY STUDY TEAM MEMBERS:

